3.0 Eligibility of Subjects

Inclusion:

- Patients ≥ 18 years of age undergoing elective open sarcoma resection for potentially curative intent who would otherwise be treated with QL block + IV-PCA converted to oral pain meds [non-narcotic bundle + opioid pain pill].

Exclusion:

- Patients with current or past substance [drug or alcohol] abuse disorder
- Laparoscopic or minimally invasive surgery
- Cases in which *anticipated* discharge is on or before postoperative day 4

4.0 Research Plan and Methods

This is a **single-center pragmatic phase II open-label randomized controlled trial** to compare two standardized bundles of usual care for postoperative pain management. The single difference in intervention is an additional QL block on POD4 in patients undergoing sarcoma surgery with potentially curative intent. The **primary endpoint is the initial discharge prescription OME**. Patients will be randomized with 1:1 ratio to receive either QL in OR + non-opioid bundle +/- low-dose IV-PCA (control arm) or QL in OR and QL on POD4 AM + non-opioid bundle +/- low-dose IV-PCA (experimental arm). The **randomization will occur on postoperative day 3** so that usual care will be performed intraoperatively and for the first 3 days after surgery. On POD3, at the time of randomization, patients will be stratified based on preoperative use of long-term opioids (e.g. extended or continuous release) (yes vs. no) and preoperative average daily OME use ($>7.5\text{mg}$ vs. $\leq7.5\text{mg}$ OME, which allows 1 tramadol, 1 oxycodone, or 1 hydrocodone per day in the lower stratum) in the 7 days before surgery. Patients will further be stratified by whether they undergo nephrectomy (yes vs. no) as part of their operative procedure, or if they have a previous surgical history of nephrectomy, as this would impact their eligibility for some of our frequently used adjunct pain medications (e.g. Celebrex, Toradol). There will be no standardization of postoperative dietary advancement, fluid management, or postoperative care, other than standardization of the IV and oral non-opioid bundle and initial IV-PCA settings in the recovery room on POD0.

Method of Group Assignment and Randomization

- **Stratified Randomization:** REDCap will be used for 1:1 allocation and stratification for preoperative long-term (≥ 3 months) opioid use (yes vs. no), preoperative average daily OME use ($>7.5\text{mg}$ vs. $\leq7.5\text{mg}$ OME), and nephrectomy status (yes vs. no), as detailed above.
- **Implementation:** Acute pain team, surgeons, advanced practice providers, fellows, and nurses will perform interventions and assessments per usual care.
- **Blinding:** This is an open-label study since the intervention arm will receive a 2nd QL block which cannot be blinded from the patient or treating physician. The allocation will be unmasked immediately upon randomization on POD3 morning after clinician rounds.

Intervention Strategy:

On postoperative day 4 [at least 96hrs from initial QL on postoperative day “0”, which is the day of surgery, per FDA guidelines], patients will undergo a 2nd QL procedure in the regular

hospital room by the Acute Pain Service attending anesthesiologist using ultrasound guidance, which is usual routine method. The intent will be to do the 2nd QL. Patients or providers may choose to forego the option if patients are already opioid-free or nearly opioid-free or for any other reasons provided by the patient.

This will be a **4-point Type I QL + subcostal block**, which allows an anterior approach to the targeted fascial layers. Using sterile technique, the attending anesthesiologist will guide the needle through the appropriate skin, subcutaneous, and muscle layers to find the right fascial plane **using ultrasound localization**. The risk of complications is virtually nil, because most hospital subcutaneous and intramuscular shots which are done blindly or by “landmark,” the QL block will be done by exact ultrasound guidance. **This block will only be done by Acute Pain Service certified faculty**. We are not studying this block’s mechanism or the drug’s mechanism – both of which are well documented in thousands of patients. **This pragmatic RCT focuses on the novel timing of using this regional block to measure its effectiveness in accelerating the opioid weaning process.**

Patients will not be randomized if anticipated to be discharged by 7am on POD4, or if they are already opioid-free on POD3 at time of randomization. The clinical team will be able to anticipate any early discharges (defined as discharge before POD4) and therefore exclude those patients from randomization.

(The **usual measures of non-opioid bundle** [including acetaminophen, NSAIDs, muscle relaxers] and conversion from IV pain meds to oral pains will be done to reduce total opioid exposure and use. Clinicians may choose to add additional non-opioids if clinically indicated. Non-opioids will be standardized for dosing, timing, and route, and will be given unless contraindicated (e.g. holding NSAIDs if nephrectomy performed for the sarcoma resection).

The 2nd block is a “Rescue Block” which we currently utilize on the floor for patients with pain control issues that are not making the anticipated progress, on postoperative day 4, and if we want to avoid opioids due to traditional concerns like ileus, somnolence, and nausea. Thus, in terms of hospital billing, this is well within the spectrum of usual care. **No component of this trial is experimental. All components are within usual care, except both arms are standardized to minimize variation for the clinical teams.**

There will be no sham procedure in the control/comparison arm. In other words, there will not be any subcutaneous injection of placebo drug in patients in the comparison arm, since this is a study of treatment sequencing rather than one focused on the drug itself. A sham procedure would be required if we were using an experimental drug in the intervention arm, but the analgesic effect of liposomal and regular bupivacaine is well-proven already. The “treatment” herein is the bundle of standardized non-opioids and the clinical care that is typically given for weaning pain medications through an inpatient stay. The only difference between the 2 arms is that the “intervention” arm has the option (patient may refuse if they are already off opioids) for the rescue block while the “comparison” arm has to use the (strictly bundled) usual measures to continue weaning opioids.

Pain measurement: Pain scores will be measured using usual care – visual analog scale by hospital inpatient nurses. They ask the patient every 4hrs on a scale 0-10, and this is documented in the EHR. Nurses then offer patients with symptomatic scores additional oral or IV pain meds as appropriate based on usual clinical care (IV if not eating or severe breakthrough pain) and oral if eating and pain is not urgent.

- **Liposomal bupivacaine - 72-hr action**
 - No repeat in 96 hrs per drug label
 - Rarely completely enough for pain control - often needs low-dose IV-PCA as well, but can reduce total opioid use if an opioid-sparing bundle is standardly used, which we will do (both arms get the same non-opioid bundle in hospital and upon discharge).
 - **Dosage instructions in Figure 3 below.** The Operating Room pharmacy has calculated the appropriate max dose of long-acting and short-acting bupivacaine, which can be safely mixed. There are laminated placards in every operating room as protective measures to prevent dosage miscalculations, and most nurses know the mixture. The Acute Pain Service attendings know as well since they have performed thousands of these injections in the past few years at our institution.
 - **Liposomal bupivacaine has become our standard of care for open surgery.** We use this in the majority of our open abdominal cancer surgery patients, while an ever-decreasing minority still get epidurals. There is extensive experience using liposomal bupivacaine for regional blocks. This RCT does not focus on the use of the block per se (since it is routine or usual care), but rather the timing of it.

Comparison Strategy:

The comparison arm patients will have usual care with just the single QL using ultrasound guidance placed in the OR. When the liposomal bupivacaine wears off, **there will be no second QL block.** The **usual measures of non-opioid bundle** [including acetaminophen, NSAIDs, muscle relaxers] and conversion from IV pain meds to oral pains will be done to reduce total opioid exposure and use.

Decision on Discharge Opioid Prescription

To avoid bias in one arm or the other, all discharge prescriptions will be standardized. Both arms will get standard non-narcotic bundles of acetaminophen 650mg q6hrs, celecoxib 100mg q12hrs, and methocarbamol 250-500mg q8hrs. Slight dose variations can be allowed here based on pharmacy availability (e.g. recent national shortage of methocarbamol 500mg pills). Patients who undergo nephrectomy will not receive celecoxib due to risk of renal insufficiency. To standardize the opioids, we will use a multiplier of 5x the last-24hrs OME count. This 24-hr count can be easily found in the electronic health record and will be taken from the time of final discharge prescription writing. If this is POD4, it will be calculated after the 2nd block, if one is administered. We chose 5x because the CDC recommends 7 days max prescription and less than 200mg OME. All patients have

clinic appointments within one week of discharge and have phone numbers to call if their multimodal pain management plan is insufficient. The chance of this is very low considering these patients are on the same plan on discharge as they have been in the last 24hrs in the hospital.

Interim Analyses:

One interim analysis will be performed when half of the patients (n=42) have been randomized. The trial will be stopped due to futility if the p-value is >0.732 for the primary endpoint.

- **Anticipated Results:**

- **Participant Flow Diagram: see Figure 1**

- **Recruitment**

All patients meeting eligibility criteria above will be recruited from clinic either during the consultation meeting or during any of the follow-up or preoperative meetings. Information regarding the trial may be sent to patients outside of clinic in order to provide time for answering questions before consent. Prior to these meetings, the patients may be sent a letter through MyChart (Appendix E) requesting permission to seek financial clearance in advance to avoid delays should the patient agree to participate in the study. An informational flyer may also be distributed to potential participants (Appendix F).

- **Generalizability**

The chosen regional block is a well-documented procedure in the anesthesia literature. The drug used in the block is universally available for other types of block. The non-narcotic bundle consists of generic drugs with minimal costs and are all well within usual care guidelines. The postoperative care pathways are published and reproducible.

Potential Harms/Adverse Events:

- Because regional blocks with liposomal bupivacaine are usual care and have been performed in thousands of MD Anderson Cancer Center patients, there are almost no clinically relevant adverse events that we anticipate besides the “trouble” of collecting the equipment, gathering the Acute Pain Service, and asking the patient to lie flat in bed for 30min on POD4. This is an extra procedure at bedside on POD4.
- There could be pain and anticipatory anxiety for the bedside procedure.
- Hematoma from needle sticks are possible but almost never seen.
- There is the cost of the procedure which is a “rescue block,” which we have used before for failed 1st time blocks. **We have typically not used it as a supplemental block to facilitate weaning patients down to zero opioids, because being completely opioid-free has never been a priority.** The reality is that it is “easier” to just order oral opioids on POD4 and beyond rather than going to the “trouble” of doing a bedside procedure on POD4 to potentially reduce opioid use.

- Unblinded providers may affect discharge OME in one arm over another. We will minimize this using 2 methods to protect patients:
 - Standardized IV-PCA settings will be used starting in the recovery room immediately out of the operating room. Unless there is an allergy, we will use our standard medication, dilaudid 0.1mg IV q 10min as needed, with no basal dose. This can be adjusted based on clinical needs. This will be weaned off when the patient starts solid food diet.
 - Patients' daily pain scores (checked by nurses q4hr) will be used to ensure that adequate pain control is prescribed before discharge. There is no "threshold" score that will be used since one patient's "4" is different than another patient's "4," but the trend will be useful to ensure patients are not being ignored. More importantly, all patients will be judged by their activities of daily living on the last 24hrs to ensure pain control is adequate.
 - **The number of opioid pills will be formulaic to avoid bias** by clinicians or patients in one arm or the other - **we will take the last 24hrs of inpatient OME used and multiply by a factor of 5x to make this number standardized between the 2 arms. This will be calculated at the time of discharge prescription writing and after the 2nd block for patients in the intervention arm if discharge date is POD4.**
 - Both arms get the same non-opioid pain management bundle for inpatient and discharge.
- **Prospective AE Records**
 - Inpatient advanced practice providers (nurse practitioner or physician assistant) will document complications daily, prospectively.
 - **Hospitalization, 30-day, and 90-day complications will be prospectively recorded** into a Sarcoma Surgery Quality Improvement Database.
- **Safety Review**
 - The study will be monitored by the MDACC Data and Safety Monitoring Board (DSMB).
 - At the time of interim futility analysis (N=42, randomized), we will also assess the length of stay for each arm. The trial will be terminated if the median LOS in the intervention arm is $\geq 25\%$ longer than the median LOS in the comparison arm. We assume that the extended LOS was caused by higher complication rate, thus leading to deviation from the usual pathway and anticipated LOS.

Figure 1. Study schema

Proprietary Information of MD Anderson

2019-0780
March 30, 2021
Protocol v.05 – Page 11

[figure not shown]

Figure 2. Study intervention timeline

[figure not shown]
Day of surgery is called postoperative day “0” and the 1st day after surgery is called postop day 1. This is different than medical terminology in which the “count” of hospital days starts at “1,” not “0” as with surgery.

- +- 1 week for outpatient follow up.
- During outpatient timepoints, survey may be administered via phone, email, or in clinic.
- MDADI-GI on DC can be collected from DC to the first post-OP visit via phone, email, or in clinic.

Figure 3. Liposomal bupivacaine mixture recommendations from OR Pharmacy [approved 2 years ago]

When mixing Bupivacaine HCl with Exparel, do not exceed a 1:2 ratio of Bupivacaine HCl:Exparel. The maximum 1:2 ratio is 150 mg Bupivacaine HCl:266 mg Exparel.

Below are the maximum 0.5% and 0.25% Bupivacaine HCl amounts when mixing with Exparel:

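### The discharge celecoxib exception omits patients with a past nephrectomy, a group that the stratification text flags for the same drug

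*Combined protocol and SAP*

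**What the plan says.** All the relevant text is in section 4.0 (Research Plan and Methods).

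- **Stratification (opening paragraph).** "Patients will further be stratified by whether they undergo nephrectomy (yes vs. no) as part of their operative procedure". The sentence goes on to a second group: "or if they have a previous surgical history of nephrectomy, as this would impact their eligibility for some of our frequently used adjunct pain medications". The drugs given as examples are "e.g. Celebrex, Toradol". The randomization list below it refers back to this definition: "nephrectomy status (yes vs. no), as detailed above".
- **Inpatient rule (Intervention Strategy).** Standardized non-opioids "will be given unless contraindicated (e.g. holding NSAIDs if nephrectomy performed for the sarcoma resection").
- **Discharge rule (Decision on Discharge Opioid Prescription).** The default is "Both arms will get standard non-narcotic bundles of acetaminophen 650mg q6hrs, celecoxib 100mg q12hrs", plus methocarbamol. The one exception by patient type is "Patients who undergo nephrectomy will not receive celecoxib due to risk of renal insufficiency". The paragraph opens by declaring every discharge prescription standardized. The only flexibility it names for the bundle is small dose changes when pharmacy supply requires them.
- **Continuity (end of the same subsection).** Patients are described as leaving hospital on the plan they followed during their final 24 hours there.

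**The concern.** The protocol identifies a group of patients, gives a reason for identifying them, and then does not carry that reason into the rule where it would act. The stratification text says that a past nephrectomy bears on eligibility for celecoxib (Celebrex). The discharge rule gives renal insufficiency as the ground for withholding celecoxib, yet words the exception so that it reaches only those having a nephrectomy. Staff who follow the discharge text literally would prescribe celecoxib to a patient whom the protocol has already marked as a doubtful candidate for it.

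What is at stake is patient safety and the clarity of an order that is meant to be applied uniformly. A lesser consequence is that the nephrectomy = yes stratum contains some patients with a written celecoxib exception and some without one, so the stratum cannot be read as a marker of NSAID eligibility, although the reason given for it invites that reading.

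**Working it through.** The plan states no figure on this point and none can be derived, so the check is a comparison of the texts.

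**Step 1. Three kinds of patient under each text as written.**

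| Patient | Stratum | Inpatient NSAID | Discharge celecoxib |
|---|---|---|---|
| Nephrectomy at this operation | yes | held (the named example) | excepted |
| Past nephrectomy, none now | yes | open: depends on whether judged contraindicated | given; no exception applies |
| Neither | no | given unless contraindicated | given |

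The inconsistency lies in the second row.

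**Step 2. Can the discharge exception be read to include past surgery?** The stratification sentence uses the verb undergo for the current procedure and adds surgical history as a separate alternative. The discharge sentence repeats only the first of these. Read by the protocol's own usage, it does not cover history.

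**Step 3. Does another rule remove the group?** Section 3.0 excludes substance abuse disorder, minimally invasive surgery and early anticipated discharge. It excludes neither past nephrectomy nor reduced renal function. The discharge subsection has no clause on contraindications. No other section says how these patients are handled at discharge.

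**Step 4. Does the inpatient rule settle it?** That rule is general, and nephrectomy for the resection is only an example, so a past nephrectomy may fall under it. There are two cases.

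- If the NSAID is held in hospital, the discharge rule as written adds celecoxib on leaving. That does not fit the description of patients going home on their last-24-hour plan.
- If the NSAID is not held in hospital, the reason given in the stratification text is not applied at either stage.

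In both cases some part of section 4.0 does not agree with another.

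**Step 5. Does it reach the primary endpoint?** The discharge opioid prescription is 5 × the OME used in the last 24 hours, counted when the final prescription is written. Discharge celecoxib is taken after that count, so it cannot alter it.

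**Step 6. Does it bias the comparison?** The bundle rule is the same in both arms, allocation is 1:1, and nephrectomy status is a stratification factor. No systematic difference between arms follows, for the primary endpoint or for later outcomes such as 30-day total OME.

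**The case against.** The best defence is that section 4.0 should be read as a whole. Inpatient non-opioids are subject to a general contraindication rule, the bundle is said to be the same in hospital and at discharge, and patients go home on their last-24-hour plan. A clinician who withheld an NSAID in hospital would then be expected to withhold it at discharge too. This has some force and makes a literal misapplication less likely. It does not close the gap: the statement about the discharge plan is descriptive, and it sits beside a prescriptive rule with a fixed regimen and one named exception.

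Several stronger readings are tempting, and the documents do not support them.

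- **That the inpatient hold also covers only nephrectomy at this operation.** It does not. That case is introduced as an example of a general rule.
- **That the protocol issues contradictory instructions.** The stratification text says eligibility is affected but gives no instruction to give or withhold a drug. The discharge exception omits a flagged group; there are not two opposite orders.
- **That the primary endpoint is affected.** Uneven inpatient NSAID use could influence last-24-hour opioid use, but the gap is in the discharge rule, which acts later.
- **That the bundle was promised to be identical within a stratum.** The promise is that it is the same between arms.
- **That a number of affected patients can be stated.** Any figure would be an assumption to which the documents give no support.

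**Conclusion.** The point holds as an inconsistency in the discharge rule. Followed as written, that rule gives celecoxib (100 mg every 12 hours, so 2 × 100 = 200 mg a day) to patients with a past nephrectomy and none at this operation, a group whose eligibility for that drug the protocol itself questions. The conclusion rests on the ordinary reading of undergo, which the protocol's own stratification sentence supports, and on the absence of any contraindication clause in the discharge subsection.

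Its importance is for safety. The sample size, the primary analysis and the comparison between arms are untouched. The number of patients concerned is unknown. This review takes no position on whether these patients should receive the drug.

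**What to change.** Reconcile four parts of section 4.0: the stratification definition, the inpatient contraindication rule, the discharge celecoxib exception, and the statement that discharge treatment continues the last-24-hour plan. Either of two outcomes would make them consistent:

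1. The discharge exception and the inpatient rule are worded to agree with the definition of nephrectomy status used for stratification.
2. If the discharge exception is deliberately narrower than the stratum, the protocol says so and corrects the reason given for including past nephrectomy in the stratum.

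The investigator and pharmacy decide which patients the exception covers. The cost is a one-sentence amendment and a check that the order set matches it. No extra patients, procedures or analyses are needed.

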5.0 Statistics and Justification of Sample Size

For the primary analysis, we will perform two-sample t-test to compare the mean doses of **discharge prescription OME** between the two groups. In addition, multiple linear regression analysis will be carried out to assess the difference between the two arms after adjusting for the stratification factors and other patient characteristics at baseline. Similar analyses will be performed for other continuous secondary outcomes such as total length of stay, 30-day total OME, initial discharge pain prescription dosage/size, number of postoperative days until zero opioid use, etc. Logistic regression analyses will be performed for binary secondary outcomes, such as discharge prescription OME = zero, discharge Rx dosage/size total OME <200mg (yes vs. no), opioids use at POD 30 (Y/N), etc. For repeated measures, linear mixed model will be used for continuous outcomes such as daily inpatient pain scores and GEE model will be fit for binary outcomes such as opioid use at various time points. Other statistical analyses may be performed as appropriate.

Based on historical data as of August 2019, the **mean discharge OME** for the comparison arm was about **200 mg (standard deviation 200mg)** and we anticipate that with a **second, repeat QL block**, the discharge OME for the intervention arm will reduce to **75 mg**.

Under this assumption and assuming a common SD of 200, the study will require 84 patients (42 in each arm) in order to have 81% power to detect the difference in discharge OME with a two-sided 5% significance level. East 6 was used for the sample size calculation. Assuming a liberal 20% dropout rate, a total of 106 patients will be enrolled from our single institution. Based on our historical operation volume of 120 patients per year, we anticipate the ability to complete enrollment within 1 year of opening the protocol. One interim analysis will be performed when half of the patients (N=42) have been randomized. The trial will be stopped due to futility if the p-value is >0.732.

- Power and significance: 81% power ($\beta=0.19$) and $\alpha=0.05$ (two-sided)
- Baseline estimate of mean comparison/control arm: 200mg OME
- Estimate of mean experimental arm: 75mg OME
- Sample size per arm: 42 pts
- Assume 20% dropout: 53 per arm
 - [1 year to complete enrollment]

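### The primary t-test ignores the randomisation strata; a pre-specified adjusted model that also includes pre-randomisation OME costs little and gains power if those covariates predict discharge OME

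*Combined protocol and SAP*

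**What the plan says.** Section 5.0 names the primary test: "For the primary analysis, we will perform two-sample t-test to compare the mean doses of" discharge prescription OME. It continues: "In addition, multiple linear regression analysis will be carried out to assess the difference between the two arms after adjusting for the stratification factors" and for other baseline characteristics, which are not listed. The adjusted analysis is therefore planned, but as an addition.

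Section 4.0 stratifies the 1:1 randomisation on long-term opioid use, preoperative average daily OME (above 7.5 mg or not) and nephrectomy. The first factor is defined in two ways. The opening paragraph says "patients will be stratified based on preoperative use of long-term opioids (e.g. extended or continuous release"), while the randomisation subsection says "preoperative long-term (≥ 3 months) opioid use (yes vs. no").

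Randomisation takes place on POD3, and patients are not randomised "or if they are already opioid-free on POD3 at time of randomization". The endpoint is formulaic: under the discharge prescription rule in Section 4.0, "we will use a multiplier of 5x the last-24hrs OME count". There is one interim look at 42 randomised patients: "The trial will be stopped due to futility if the p-value is >0.732 for the primary endpoint".

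**The concern.** Two separate losses of efficiency are possible.

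**Strata.** Stratified randomisation removes most of the between-arm imbalance in the stratification factors. If those factors predict discharge OME, the difference in means becomes less variable. The t-test's standard error still contains the between-stratum variance, so the test is conservative: its true type I error falls below 5%, and it has less power than a model that includes the strata.

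**Pre-randomisation OME.** OME over the 24 hours before POD3 randomisation is an earlier reading of the quantity that, multiplied by five, becomes the endpoint. It is not a stratification factor, so leaving it out does not disturb the error rate. It can only cost power.

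With 84 analysed patients and 81% planned power there is little to spare. A second cost is ambiguity: an open-label trial will have two planned estimates of the same effect, one with an open covariate list.

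**Working it through.** **Inputs from Section 5.0:** means 200 and 75 mg (difference 125 mg), common SD 200 mg, 42 per arm, two-sided 5%. **Assumed:** the share of outcome variance explained (R²), stratum prevalences and block size, none of which the documents give.

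**1. The plan's own figure.** Noncentrality = 125 / (200 × √(2/42)) = 125 / 43.64 = 2.864. With 82 degrees of freedom the critical value is 1.989 and power is **80.8%**, in agreement with the stated 81%.

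**2. Strata-adjusted model.** The residual SD becomes 200 × √(1 − R²), so the noncentrality is 2.864 / √(1 − R²), with 82 − 3 = 79 degrees of freedom. The t-test's true alpha, if the strata were perfectly balanced, is 2 × [1 − Φ(1.96 / √(1 − R²))].

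| Strata R² (assumed) | Noncentrality | Adjusted power | t-test alpha, perfect balance |
|---|---|---|---|
| 0% | 2.864 | 80.8% | 5.0% |
| 5% | 2.939 | 82.7% | 4.4% |
| 10% | 3.019 | 84.7% | 3.9% |
| 20% | 3.202 | 88.6% | 2.8% |
| 30% | 3.423 | 92.2% | 1.9% |

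**3. Simulation with realistic balance.** Stratified blocks of 4 or 8, prevalences of 10/20/40% or 30/30/40%, normal and skewed errors, 10,000 replicates per scenario:

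| Strata R² | t-test alpha | t-test power | Adjusted power |
|---|---|---|---|
| 0% | about 5% | 81% | 80–81% |
| 5% | 4.3–4.9% | 81% | 82–83% |
| 10% | about 4% | 82% | 84–85% |
| 20% | 3.2–3.4% | 83% | 88% |
| 30% | 2.3–3.1% | 83–85% | 91–92% |

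The adjusted model's alpha stayed at 4.4–5.3%. The gain is within noise at R² of 5% or less, about 2–3 points at 10% and about 5 points at 20%.

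**4. Adding pre-randomisation OME** (78 degrees of freedom). If it explains a further 20%, analytic power at strata R² of 0/10/20/30% is 88.5/92.2/95.5/97.9%, about 6–8 points above the strata-only model. A further 10% adds about 3–4 points. With strata R² of 0 and this covariate at 20%, the simulated t-test alpha is 5.1%, so omitting it does not affect size.

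**5. Cost if nothing is prognostic.** The four degrees of freedom alone take power from 80.80% to 80.75%. Chance imbalance matters more. Giving no credit for stratification, the variance inflates by 1 + 4/(84 − 4 − 3) = 1.052 and power is 78.8%, a loss of 2 points; break-even R² is then about 5%. Simulations with stratified blocks lost about 0.5 to 1.6 points.

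**6. Futility look at n = 42, stopping if p > 0.732** (all 42 outcomes assumed available). With no effect, the t-test stops 26–30% of trials and the strata-adjusted model 25–28%. With a true 125 mg difference, the t-test and the adjusted model stop 3.6% and 3.9% at R² = 0, 3.0% and 2.5% at 20%, and 2.8% and 1.8% at 30%. The boundary behaves similarly under either model.

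**The case against.** The plan contains no error here. It names a valid test, sizes the trial for that test and already commits to the strata-adjusted regression, so what remains is which analysis is called primary and one further covariate. That is right, and it limits the weight of the point.

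The gain also cannot be read from the documents, and at a strata R² of 5% or less it is negligible. This stands.

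The case for POD3 OME is uncertain. The 24 hours before randomisation fall largely within the first block's 72-hour action, IV-PCA may still be running, discharge may be days later, and excluding opioid-free patients narrows the covariate's range. Section 2.0 links prescriptions to use in the last 24 hours before discharge, not to use on POD3. The plan checks opioid-free status on POD3; that a 24-hour milligram count is recorded then is an inference. All of this limits the expected gain, but the cost of including the covariate remains small.

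Finally, the figures above assume an additive effect and a common SD. With lognormal data (mean 200, SD 200 mg) and a proportional effect of the planned size, both methods had about 99% power and adjustment gained almost nothing. For a smaller proportional effect of about 80 mg with prognostic covariates, the gain returned: 66% for the t-test against 77% adjusted.

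**Conclusion.** The concern holds as a conditional improvement that should be made. The t-test does not inflate false positives and the 81% power is correct. Under the plan's additive, common-SD assumptions, promoting the strata-adjusted model gains about 2–3 points of power at a strata R² of 10% and about 5 at 20%, and keeps the error rate near its nominal 5%. With strata at 10% and pre-randomisation OME at a further 20%, simulation gave about 91–92% against 82%. The downside is about 1 to 2 points if no covariate predicts the outcome. Every R² is an assumption, so confidence in the size of the gain is moderate at best; the direction is clear.

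**What to change.** - Make the primary analysis a linear model of discharge OME on arm, the three stratification factors as entered at randomisation, and OME in the 24 hours before POD3 randomisation, tested at two-sided 5%. The estimate remains a mean difference in mg.
- Keep the unadjusted t-test as a supportive analysis.
- Name any other baseline covariates and confine them to exploratory models. Fix all covariates and their coding before outcome data by arm are seen. A longer list costs more: with six covariates that predict nothing, power is 77.7% without credit for stratification.
- State that the interim futility p-value comes from the same model, after rechecking the operating characteristics of the 0.732 boundary.
- Reconcile the two definitions of the long-term opioid stratum in Section 4.0 before using it as a covariate.

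The cost is a change of wording in Section 5.0, one more 24-hour OME count from the health record, the boundary recheck and four degrees of freedom. No additional patients are needed.
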